11.3 RANDOMIZATION AND BLINDING

This is an open-label, single arm, Phase 1b / 2 study; thus, randomization and blinding are not part of the study design.

11.4 ANALYSIS POPULATION SETS

This study will have three analysis populations:

- **Intent-to-Treat (ITT)** analysis set includes all patients who were enrolled into the study.
- **Safety Analysis Set** consists of all patients who received study treatment (alvocidib).
- **Response Evaluable Set** consists of patients who have at least one post-baseline efficacy assessment; patients without a post-baseline efficacy assessment will not be considered evaluable for the primary efficacy analysis. Patients who discontinue due to disease progression or die or treatment-related toxicity prior to having a disease assessment will be included in the Response Evaluable population.

11.5 PATIENT DISPOSITION

A detailed description of patient disposition will be provided. It will include:

- The number of patients who were enrolled, included in the ITT, safety, and response evaluable analysis sets.
- A summary of patient dose cohorts.
- A summary of patients who complete the protocol.
- A summary of reasons for withdrawal from study.
- A summary of reasons for patients with treatment failure.
- An account of all identified protocol violations.
- All patients enrolled in the study will be accounted for in the summation.

11.6 DEMOGRAPHIC AND BASELINE CHARACTERISTICS

Demographic characteristics including age, gender, race, and ethnicity will be presented in the form of tabular summary statistics. Other subject baseline characteristics including but not limited to: weight, height, body surface area, initial stage of disease, prior therapies, and ECOG performance status will be presented similarly.

11.7 CONCOMITANT MEDICATIONS

The number and proportion of patients using different concomitant medications will be tabulated and summarized by WHO Drug anatomical therapeutic chemical (ATC) and preferred term.

11.8 TREATMENT ADMINISTRATION / COMPLIANCE

Study drug administration will be described in terms of the total number of cycles administered, the median (range) of cycles administered, dose intensity, and reasons for the deviations from planned therapy.

11.9 EFFICACY ANALYSIS

The efficacy endpoints include the following:

- Complete Response Rate (CRR) is the percentage of patients achieving a CR, CRi, CRmarrow, PR, or HI. Patients who, for any reason, do not supply bone marrow for response assessment are counted among those not achieving CR/CRi/CRmarrow/PR/HI. CRR will be summarized by number and percentage of patients meeting the definition of CRR along with the corresponding exact 95% confidence intervals.
- Duration of response and time to AML will be summarized by Kaplan-Meier methods (median, 95% CI, number of events, number censored, and Kaplan-Meier figures),
- Hematological improvement and rate of transfusion independence will be summarized using the appropriate descriptive statistics and 95% confidence intervals.
- Overall survival (OS), defined as the time from first dose to death from any cause. OS will be summarized by Kaplan-Meier methods (median, 95% CI, number of events, number censored, and Kaplan-Meier figures).

Descriptive statistics will also be calculated for each secondary measure of efficacy.

- The proportion of MDS patients in the overall population achieving RBC transfusion independence with duration ≥ 84 days (12 weeks) during treatment. Baseline RBC transfusion dependency is defined as an average transfusion requirement of ≥ 2 units/28 days of RBCs without any consecutive 28-day gaps between transfusions for a minimum of 56 days immediately preceding first dose. Transfusion data include the hemoglobin value for which the transfusion was administered and must have been ≤ 10.0 g/dL within 7 days prior to transfusion administration to be counted toward the RBC transfusion-dependent status.
- Platelet transfusion independence with duration ≥ 84 days (12 weeks) will be assessed in the proportion of patients who were platelet transfusion-dependent at baseline. Baseline platelet transfusion requirements are established by the number of platelet transfusions administered during the 56 days immediately preceding and including the date of first dose.

- Erythroid hematologic improvement and platelet hematologic improvement will be assessed according to the 2006 revised IWG criteria [28].

Additional analyses may be performed to assist the sponsor in planning future studies.

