5.2.2.6 Cycles 2+ – Day 28 (+1/-3 Days)

Perform the following evaluations on Day 28 of every EVEN cycle (ie, Cycle 2, Cycle 4, etc):

- Perform bone marrow biopsy and aspiration and collect peripheral blood sample for assessment of response ([Appendix F](#)), standard cytogenetics, and PD analyses ([Section 7.4](#), [Table 9](#) and [Table 10](#);

Appendix E). [Note with a +1/-3 day window, these may be performed on Days 25-28 or Day 1 of the next cycle. If performed on Day 1 of the next cycle, please collect bone marrow and aspiration as well as peripheral blood samples prior to administering first dose of DEC or AZA]

- If the bone marrow biopsy and/or aspirate is nonproductive or not diagnostic, at the EVEN 2+ cycle visits, there should be no delay in dosing and the procedure should be repeated within 7 days.
- Six to 8 bone marrow slides will be prepared (in addition to fresh bone marrow samples) and sent to the Sponsor.
- Response assessments **with** standard cytogenetics **and** blood sample collection for PD analyses should be repeated on Day 28 (+1/-3 days) of Cycles 2, 4, and 6, and then every 4 cycles, thereafter, or as clinically indicated. If medically appropriate, response assessments should be repeated at the time of disease progression.
- Assess for AEs
- Record only those medications (prescription, nonprescription, nutritional supplements) administered in conjunction with an AE.

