APPENDIX F – INTERNATIONAL WORKING GROUP (IWG) RESPONSE CRITERIA (2006) (CONT)

Hematologic improvement*	Response criteria (responses must last at least 8 wk)†
Erythroid response (pretreatment, < 11 g/dL)	Hgb increase by ≥ 1.5 g/dL Relevant reduction of units of RBC transfusions by an absolute number of at least 4 RBC transfusions/8 wk compared with the pretreatment transfusion number in the previous 8 wk. Only RBC transfusions given for a Hgb of ≤ 9.0 g/dL pretreatment will count in the RBC transfusion response evaluation†
Platelet response (pretreatment, $< 100 \times 10^9/L$)	Absolute increase of $\geq 30 \times 10^9/L$ for patients starting with $> 20 \times 10^9/L$ platelets Increase from $< 20 \times 10^9/L$ to $> 20 \times 10^9/L$ and by at least 100%†
Neutrophil response (pretreatment, $< 1.0 \times 10^9/L$)	At least 100% increase and an absolute increase $> 0.5 \times 10^9/L$ †
Progression or relapse after HI‡	At least 1 of the following: At least 50% decrement from maximum response levels in granulocytes or platelets Reduction in Hgb by ≥ 1.5 g/dL Transfusion dependence

Deletions to the IWG response criteria are not shown.

To convert hemoglobin levels from grams per deciliter to grams per liter, multiply grams per deciliter by 10.

Hgb indicates hemoglobin; RBC: red blood cell; HI: hematologic improvement.

*Pretreatment counts averages of at least 2 measurements (not influenced by transfusions) ≥ 1 week apart (modification).

†Modification to IWG response criteria.

‡In the absence of another explanation, such as acute infection, repeated courses of chemotherapy (modification), gastrointestinal bleeding, hemolysis, and so forth. It is recommended that the 2 kinds of erythroid and platelet responses be reported overall as well as by the individual response pattern.

[28]

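### In the composite response rate of protocol Section 11.9, a missing marrow cancels hematologic improvement, which Appendix F defines from blood counts and transfusions alone

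*Protocol*

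**What the plan says.** Protocol Section 11.9 gives the composite: "Complete Response Rate (CRR) is the percentage of patients achieving a CR, CRi, CRmarrow, PR, or HI". HI alone is thus enough to make a patient a responder. The next sentence in the same bullet is the missing-marrow rule: "Patients who, for any reason, do not supply bone marrow for response assessment are counted among those not achieving CR/CRi/CRmarrow/PR/HI".

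The HI table in protocol Appendix F uses peripheral blood and transfusion data only. The erythroid response is a hemoglobin rise or a fall in transfusions ("Relevant reduction of units of RBC transfusions by an absolute number of at least 4 RBC transfusions/8 wk"), with a restriction on which transfusions count ("Only RBC transfusions given for a Hgb of ≤ 9.0 g/dL pretreatment will count in the RBC transfusion response evaluation"). The platelet and neutrophil responses are changes in the counts. The duration condition is "responses must last at least 8 wk". The table contains no marrow condition.

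Other places bear on how far the rule reaches:

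- Section 11.9 also reports HI on its own: "Hematological improvement and rate of transfusion independence will be summarized using the appropriate descriptive statistics and 95% confidence intervals". It further assesses erythroid and platelet HI by the 2006 IWG criteria. Neither bullet carries the marrow condition.
- Section 11.2 counts HI as a response in the Simon design. Its own rules make withdrawal for treatment-related toxicity or progression, or death, before evaluation a non-response. Other drop-outs before assessment are unevaluable and may be replaced.
- Section 11.4 makes a patient evaluable on any post-baseline efficacy assessment, without naming a marrow.
- Section 5.2.2.6 sets the marrow timing ("Perform the following evaluations on Day 28 of every EVEN cycle"), with response assessments at Cycles 2, 4 and 6 and then every 4 cycles.
- SAP Section 11 does not repeat the rule. It leaves HI out of its best-response categories and presents HI in listings.

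**The concern.** Counting a missing marrow as failure is coherent for categories that need a marrow. Extending it to HI is not, because HI can be fully documented from blood counts and transfusion records that the protocol collects throughout treatment. The same patient then has two different outcomes under two parts of one protocol.

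Two things are at stake. CRR is a secondary objective in both phases, and the composite would understate response. If the Simon count is derived in the same way, HI-only responders without a marrow would also drop out of the two responses needed to open Stage 2 and the six of 25 needed for a positive conclusion. Power would then be lower than stated.

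**Working it through.** **Inputs from the protocol (Section 11.2).** Null rate 10%, alternative 30%. Stage 1 has 15 patients and stops at 1 or fewer responders. The total is 25 patients, with success at 6 or more. Stated type I error is 0.05 and power 80%.

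**Reproducing the stated figure.** With X1 the Stage 1 responders and X2 the responders among the 10 Stage 2 patients,

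P(success | p) = Σ over x = 2 to 15 of P(X1 = x) × P(X2 ≥ 6 − x).

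At p = 0.30 the terms for x = 2, 3, 4 and 5 are 0.0321, 0.1050, 0.1860 and 0.2003. For x ≥ 6 success is already certain, which adds P(X1 ≥ 6) = 0.2784. The sum is 0.802, so the stated 80% reproduces. At p = 0.10 the same formula gives 0.033, so 0.05 is the design ceiling and not the attained level. The chance of stopping at Stage 1 is 0.549 at 10% and 0.035 at 30%.

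**Effect of the marrow rule, if it governs the Simon count.** Let h be the share of responders who are HI-only, and m the share of those HI-only responders with no response marrow. The documents give neither, so both are assumptions. The countable rate is p × (1 − m × h), and the same factor scales the null rate.

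| m | h | Countable rate at true 30% | Power | Type I error (true 10%) |
|---|---|---|---|---|
| 0 | any | 30.0% | 0.802 | 0.033 |
| 0.02 | 0.3 | 0.30 × (1 − 0.006) = 29.8% | 0.796 | 0.032 |
| 0.05 | 0.7 | 0.30 × (1 − 0.035) = 28.95% | 0.769 | 0.028 |
| 0.10 | 0.3 | 0.30 × (1 − 0.03) = 29.1% | 0.774 | 0.029 |
| 0.20 | 0.7 | 0.30 × (1 − 0.14) = 25.8% | 0.651 | 0.017 |

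Power falls and type I error falls with it, so the error is in the conservative direction.

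**Which part of the range is plausible.** HI needs 8 weeks and the first response marrow falls at about Day 56 (Day 28 of Cycle 2), so a patient who leaves before then could rarely have qualified for HI. Marrows recur, and Section 5.3 adds one at end of study if 8 or more weeks have passed since the last assessment. On a natural reading, the rule catches only a patient who supplies none of these. Missing marrows should therefore be rarer among HI responders than among all patients, which favors the 2-5% rows over the 10-20% rows.

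**Effect on a single result.** 6/25 is 24% (exact 95% CI 9.4 to 45.1) and meets the rule. 5/25 is 20% (6.8 to 40.7) and does not. One HI-only responder without a marrow is enough to move from one to the other.

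**The case against.** **HI is reported elsewhere.** A reader might infer that HI responders disappear from the efficacy results. They do not. The rule stands in the CRR bullet only, and the separate HI summaries in Section 11.9 carry no marrow condition. This stands, and it confines the point to the composite.

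**The link to the Simon count is not stated.** Section 11.2 uses the same list of responses but has its own handling of withdrawals and replacements, and Section 11.4 does not require a marrow for evaluability. A reader might take the power loss as established; the documents support it only conditionally. This stands too.

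**A nonproductive aspirate is a poor example.** A reader might think that one failed aspirate makes an HI responder a failure. Sections 5.2.2.6 and 5.3 call for both biopsy and aspiration and for a repeat within 7 days, Section 4.3.3 excludes patients with a dry tap before enrollment, and failing to supply a marrow is not the same as a failed procedure. That example should not be used.

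**Missing-as-failure is a safeguard.** In a single-arm trial it protects against selective omission of marrows, and improved blood counts cannot exclude marrow progression, which Appendix F defines partly by blasts. This justifies the rule for the marrow-based categories and is a reason to list the affected patients. It does not remove the conflict, because Appendix F sets no marrow condition for HI.

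**Little hangs on it now.** SAP Section 16 says the SAP supersedes the protocol's statistical considerations. SAP Section 2 reports no Phase 2 enrollment, and SAP Sections 1 and 15.1 rule out inferential efficacy analysis. This stands as a limit on importance.

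**Conclusion.** The conflict between Section 11.9 and Appendix F is real. Within CRR, an HI-only responder with no response marrow is scored as a failure although every HI criterion is met.

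The size is probably small. If the same derivation feeds the Simon count, power falls from 80.2% to about 77-80% with m of 2-5% and h of 30-70%. It falls to 65-77% only if m is 10-20%. These shares are assumptions, and the 65% end needs both extremes at once. A reader might infer that the design is seriously underpowered or that false positives rise. The documents support neither: the loss depends on undocumented shares and an unstated link, and type I error goes down.

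This is a minor wording defect. It still deserves correction because CRR remains a Phase 1b secondary objective in SAP Section 3.2, 20 Phase 1b patients are enrolled, and the SAP does not say how a patient with HI and no marrow is to be classified in CRR.

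**What to change.** Limit the missing-marrow sentence in Section 11.9 to CR, CRi, marrow CR and PR. State that HI is scored from blood counts and transfusion records under Appendix F whether or not a marrow was supplied. Say in Section 11.2 whether the Simon count uses this derivation. If CRR is derived for the study report, put the same statement in SAP Section 11.

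The cost is a few lines of text and no new data collection. The downside is that marrow progression cannot be excluded in an HI responder without a marrow. List those patients individually and give their number beside the CRR, so that a reader can see the result with and without them.

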3.2 PHASE 2 OBJECTIVES

Primary:

- To determine preliminary efficacy and anti-MDS activity of alvocidib administered in sequence after AZA in untreated patients with de novo or secondary MDS

Secondary:

- To assess the CRR (per 2006 revised International Working Group [IWG] criteria [28])
- To evaluate the tolerability of alvocidib when administered in sequence following AZA in this patient population
- To determine whether a defined BH3 profile predicts response to alvocidib administered in sequence after AZA in untreated MDS population
- To determine if treatment with alvocidib administered in sequence after AZA results in improvements in transfusion dependence (defined as an average transfusion requirement of ≥ 2 units/28 days of RBCs without any consecutive 28-day gaps between transfusions for a minimum of 56 days immediately preceding first dose) and/or hemoglobin level (transfusion data to include the hemoglobin value for which the transfusion was administered and must have been ≤ 10.0 g/dL within 7 days prior to transfusion administration to be counted toward the RBC transfusion-dependent status):
 - Hemoglobin increase of ≥ 1.5 g/dL without ESAs

OR

- Reduction of ≥ 4 RBC transfusions/8 weeks in comparison to pre-treatment values and lasting at least 8 weeks

Exploratory Objectives

- To assess the pharmacokinetics (PK) of alvocidib when administered in sequence after AZA
- To evaluate correlative biomarkers of therapy including, but not limited to, BH3 profiling with an emphasis on MCL-1 dependence, genetic mutations, and other biomarkers associated with MDS
- To document the percentage of patients transplanted post-treatment and outcomes post-transplant

Additional exploratory analyses may be performed, if useful, in the interpretation of the data.

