4.3.2 Inclusion Criteria

To be eligible for participation in the study, patients must meet all of the following inclusion criteria:

1. Aged ≥ 18 years
2. Phase 1b **Dose Escalation:** Patients with previously untreated MDS and patients with MDS who received fewer than six (6) cycles of previous HMAs
Phase 1b Expansion: Untreated patients with de novo or secondary MDS
Phase 2: Untreated patients with de novo or secondary MDS
3. Patients with an Eastern Cooperative Oncology Group (ECOG) Performance Status (PS) score ≤ 2 at enrollment
4. Provide written informed consent prior to any study-related procedure. (In the event that the patient is re-screened for study participation or a protocol amendment alters the care of an ongoing patient, a new informed consent form must be signed.)
5. Patients with a life expectancy of ≥ 3 months (90 days)
6. Patients with adequate major organ functions meeting the following criteria on the basis of laboratory data within 4 weeks (28 days) before enrollment (if multiple data are available, most recent data during the period):
 - a. Serum creatinine: $\leq 1.8 \times$ the upper limit of the normal (ULN) range
 - b. Total bilirubin: $\leq 2 \times$ the ULN
 - c. Aspartate transaminase (AST) and alanine transaminase (ALT): $\leq 3 \times$ the ULN

7. Be able to comply with the requirements of the entire study.

- 8. *Patients with Revised International Prognostic Scoring System (IPSS R) intermediate-, high-, and very high-risk MDS***

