6.2 REASONS FOR WITHDRAWAL

A patient may be permanently removed from the study for any of the following reasons:

- Failure to achieve a response. Patients not demonstrating evidence of CR/CRi/CRmarrow/PR/HI after the second cycle of treatment will be considered for removal from the study, although with permission of the Medical Monitor, induction treatment may continue if clinically indicated and provided there is no evidence of toxicity \geq NCI CTCAE grade 4;
- An excessive Grade 3-4 toxicity without a response to treatment or occurrence of any other AE, concurrent illness or laboratory abnormality which, in the opinion of the PI, warrants the patient's permanent withdrawal;
- Patient noncompliance, defined as refusal or inability to adhere to the study schedule;
- At the request of the patient, PI, the Sponsor, or regulatory authority;
- Patient is lost to follow-up;
- Patient becomes pregnant while on study;
- Patient begins another treatment for their disease; or
- Patient death.

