7.2 EFFICACY ENDPOINTS

Primary Efficacy Endpoints

- Assess preliminary efficacy, as determined by response rate, duration of response, hematological improvement, rate of transfusion dependence, time to AML, and overall survival.

Efficacy endpoints will be any objective response to study drug therapy using assessments defined by the 2006 revised International Working Group (IWG) criteria [28] and European MDS Working Group.

Secondary Efficacy Endpoints

- The proportion of MDS patients in the overall population achieving RBC transfusion independence with duration ≥ 84 days (12 weeks) during treatment. Baseline RBC transfusion dependence is defined as an average transfusion requirement of ≥ 2 units/28 days of RBCs without any consecutive 28-day gaps between transfusions for a minimum of 56 days immediately preceding first dose. Transfusion data include the hemoglobin value for which the transfusion was administered and must have been ≤ 10.0 g/dL within 7 days prior to transfusion administration to be counted toward the RBC transfusion-dependent status.

- Platelet transfusion independence with duration ≥ 84 days (12 weeks) will be assessed in the proportion of patients who were platelet transfusion dependent at baseline. Baseline platelet transfusion requirements are established by the number of platelet transfusions administered during the 56 days immediately preceding and including the date of first dose.
- Erythroid hematologic improvement and platelet hematologic improvement will be assessed according to International Working Group 2006 criteria.
- Correlation of complete response rates with BH3 profiling results including MCL-1 dependency
- Overall survival compared to historical data

Complete details of the planned analysis will be documented in a full Statistical Analysis Plan (SAP), which will be finalized before locking the study database.

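### The RBC transfusion-independence rate is taken over all patients and never tied to the baseline dependency it defines, so it need not equal the conversion rate in dependent patients

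*Protocol*

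**What the plan says.** Protocol 11.9 gives as a secondary measure "The proportion of MDS patients in the overall population achieving RBC transfusion independence", lasting at least 84 days during treatment. The synopsis, Protocol 7.2 and SAP 3.7.2 word it the same way. Each then defines baseline RBC dependency: an average of at least 2 units per 28 days over at least the 56 days before first dose, no 28-day gap, and a hemoglobin condition on the transfusions counted. None says what that definition is for.

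The next bullet treats platelets differently: independence "will be assessed in the proportion of patients who were platelet transfusion-dependent at baseline".

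The primary list in 11.9 also says that the "rate of transfusion independence will be summarized using the appropriate descriptive statistics and 95% confidence intervals", naming neither cell line nor denominator. Protocol 7.2 prints that item the other way round: "hematological improvement, rate of transfusion dependence, time to AML, and overall survival".

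For context:
- Phase 2 entry reads "Phase 2: Untreated patients with de novo or secondary MDS" (Protocol 4.3.2); no criterion requires transfusion dependence.
- The related Phase 2 objective is whether "alvocidib administered in sequence after AZA results in improvements in transfusion dependence" (Protocol 3.2).
- The analysis sets are ITT, Safety and Response Evaluable (Protocol 11.4, SAP 6). None is called the overall population.
- SAP 9.3 plans no subgroups, and SAP 11 gives no rule or table for transfusion independence.

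**The concern.** A patient who is not transfusion-dependent at baseline cannot become independent; such a patient can only remain so. Because eligibility admits both kinds of patient, an all-patient denominator mixes two quantities unless the numerator rule is stated, and it is not. The platelet bullet shows that the authors had the restriction available, and nothing explains why RBC differs.

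What is at stake is interpretability. A reader given a single percentage could not tell whether it counts conversions only or also patients who never needed transfusion. On either reading the figure depends on the share of patients dependent at entry, which is not a treatment effect. The one exception is the second reading when both groups have the same rate.

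**Working it through.** The documents give no target, power or assumed rate for this endpoint, so there is no stated figure to reproduce.

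**Inputs.** All three are assumptions, because the documents supply none of them:
- *d*: share of patients RBC-dependent at baseline
- *r*: share of dependent patients who reach 84 transfusion-free days on treatment (conversion)
- *q*: share of non-dependent patients with 84 transfusion-free days on treatment

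**Formulas.**
- Reading A, only converters in the numerator and all patients below: rate = d × r.
- Reading B, any patient with 84 transfusion-free days counts: rate = d × r + (1 − d) × q.
- Dependent patients only, above and below: rate = r.

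Reading B minus r equals (1 − d)(q − r). It is therefore above r if q > r, below r if q < r, and equal to r if q = r.

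**Numbers at r = 30%, with q held fixed so that only the baseline mix changes.**

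| d | A: d × r | B, q = 90% | B, q = 10% | Dependent only |
|---|---|---|---|---|
| 20% | 6% | 6 + 72 = 78% | 6 + 8 = 14% | 30% |
| 80% | 24% | 24 + 18 = 42% | 24 + 2 = 26% | 30% |

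Baseline mix alone thus moves the rate by 18 points under A (24 − 6), by 36 points under B at q = 90% (78 − 42), and by 12 points under B at q = 10% (26 − 14). At q = 30%, B stays at 30% for every d.

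**In patients.** Take the planned 25 Phase 2 patients and suppose that 10 are dependent, 3 convert, and 12 of the 15 non-dependent patients stay transfusion-free for 84 days. Reading A gives 3/25 = 12%. Reading B gives (3 + 12)/25 = 60%. The rate in dependent patients is 3/10 = 30%. One data set yields three answers, and the text does not choose between the first two.

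**The case against.** The best defense is that the denominator is in fact stated. The bullet names all patients, and because it goes on to define baseline dependency, achieving independence most naturally means conversion. On that view d × r is a coherent, conservative all-patient rate, and preferring dependent patients only is a choice of estimand. This is fair as far as it goes. The rate is still diluted by patients who cannot succeed, and the intended numerator has to be inferred.

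Second, the objective in Protocol 3.2 has its own baseline-anchored measures: a hemoglobin rise, or a fall of at least 4 RBC transfusions per 8 weeks. The erythroid criterion in Appendix F is also set "compared with the pretreatment transfusion number in the previous 8 wk". This stands. A reader might infer that the plan has no valid measure of improvement in transfusion dependence; the documents do not support that. Those measures are separate, however, and do not define this rate.

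Third, a reader might infer that the wording inflates the result. It does so only under Reading B with q above r. Since 84 days is three 28-day cycles, q might be thought low because patients without a response "after the second cycle of treatment will be considered for removal from the study" (Protocol 6.2). But that section lets them continue with the Medical Monitor's permission, the synopsis makes all patients eligible for at least 4 cycles (4 × 28 = 112 days), and the on-treatment requirement limits conversion as well. The documents settle neither q nor the direction of the distortion.

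Fourth, no output carries the rate. Protocol 11.1 plans no formal hypothesis testing, and the Simon rule counts other responses. This is correct and governs the severity.

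**Conclusion.** The point holds as a defect of definition, at low severity. The endpoint covers all patients, and its own dependency definition is left unused. The resulting rate is d × r or d × r + (1 − d) × q, and neither is the conversion rate in general.

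The sizes shown rest entirely on assumed values of d, r and q. A reader might join the extremes of Reading B and quote 14% to 78% as the effect of baseline mix. That span varies q as well; at fixed q the ranges are 42% to 78% or 14% to 26%.

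Nor do the documents support an inference that a trial result was distorted. The endpoint is secondary and descriptive and lies outside the Simon decision. The synopsis and SAP 3.7.2 place it under Phase 2, SAP 2 records no Phase 2 patients, and SAP 11 plans no table for it. The consequence is confined to the plan as written and to any later protocol that reuses the text.

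**What to change.** In the synopsis, Protocol 7.2, Protocol 11.9 and SAP 3.7.2:
- Define the endpoint as the proportion with 84 or more days of RBC transfusion independence during treatment, among patients who meet the baseline RBC-dependency definition.
- Name the analysis set from which those patients are drawn (ITT or Response Evaluable), in place of the undefined overall population.
- Report maintained independence in non-dependent patients as a separate line.
- Give the primary-list transfusion-independence item the same denominator, and correct dependence to independence in Protocol 7.2.

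The edit is wording only and reuses a definition already in the text. The cost is precision. With 10 of 25 patients dependent and 3 converting, the exact 95% interval is 6.7% to 65.2% for 3/10, against 2.5% to 31.2% for 3/25. With only 5 dependent, 1/5 gives 0.5% to 71.6%. The all-patient interval is narrower because it estimates a different quantity. Even corrected, a single-arm rate would not separate the contribution of alvocidib from that of azacitidine.
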